### 3. GENERAL INFORMATION

Objective	To evaluate refractive stability (spherical equivalent change $\leq$ 0.50D from 1-month to 3-months).  The hypothesis is that the Alcon Clareon® intraocular lens provides stable refractive stability evaluated over the postoperative 3 months with 80% of subjects achieving $\leq$ 0.50D spherical equivalent change from 1-month to 3-months.
Test Article(s)	Clareon® Intraocular lens
Control Article(s)	None.
Sample size	60 eyes of 30 subjects
Study Population	Subjects $\geq$ 50 years of age presenting for cataract surgery who are appropriate candidates for intraocular lens implantation.
Number of sites	One
Study Design	Prospective, non-randomized, single-arm study.
Masking	Evaluator masked
Variables	Primary: Refractive stability (spherical equivalent change $\leq$ 0.50D from 1-month to 3-months)  Secondary: 

• Binocular visual acuity outcomes (uncorrected and best-distance-corrected) at distance (4-6 m) and intermediate (80 cm) at 1 month and 3 months

• Percentage of patients cumulative distribution achieving 20/20 or better, 20/25 or better, 20/30 or better and 20/40 or better intermediate vision at 80 cm

• Binocular defocus curve at 3 months

Duration / Follow-up	Preoperative to 3 months postoperative

## 5. INTRODUCTION

Previous studies have shown that the Clareon® intraocular lens (IOL) (Alcon, Fort Worth, Texas, USA) provides good visual outcomes for patients at distance. We are interested in determining refractive stability when the Clareon® IOL is implanted bilaterally.

## 6. OBJECTIVE(S)

To evaluate refractive stability (spherical equivalent change  $\leq 0.50\text{D}$  from 1-month to 3-months).

## 7. SUBJECTS

### 7.1. Subject Population

Eligible test subjects will be presenting for cataract surgery and who are interested in and appropriate candidates for intraocular lens implantation.

A total of 60 eyes of 30 subjects at one site will be enrolled. Both eyes of a subject must be enrolled. Subjects must meet the inclusion criteria. Prior to enrollment, subjects will be provided information on the study and asked to sign a patient information and consent form to participate. The patient information and consent form will be approved by an appropriate ethics committee.

### 7.2. Inclusion Criteria

Subjects are eligible for the study if they meet the following criteria:

**Note:** Ocular criteria must be met in both eyes.

- Presenting for uncomplicated bilateral cataract surgery and have an interest in an IOL option
- Gender: Males and Females.
- Age: 50 or older.
- Willing and able to provide written informed consent for participation in the study.
- Willing and able to comply with scheduled visits and other study procedures.
- Have good ocular health, with no pathology that compromises visual acuity (outside of residual refractive error and cataract)
- Potential postoperative visual acuity of (20/25 Snellen) or better in both eyes

### 7.3. Exclusion Criteria

If any of the following exclusion criteria are applicable to the subject or either eye, the subject should not be enrolled in the study.

- Irregular astigmatism (e.g. keratoconus)
- Corneal pathology (e.g. scar, dystrophy, pterygium, severe dry eye)
- Previous radial keratotomies, corneal refractive surgery or other corneal surgery (e.g. corneal transplant, DSAEK, lamellar keratoplasty)
- Previous anterior or posterior chamber surgery (e.g., vitrectomy, laser iridotomy)
- Diabetic retinopathy
- Macular pathology (e.g. ARMD, ERM)
- History of retinal detachment
- Any patient based on Barrett toric calculator that will have  $\geq 0.75D$  residual astigmatism if Clareon® non-toric IOL is implanted
- Subjects who have an acute or chronic disease or illness that would confound the results of this investigation (e.g., immunocompromised, connective tissue disease, clinically significant atopic disease, diabetes, and any other such disease or illness), that are known to affect postoperative visual acuity.
- Participation in any investigational drug or device trial within the previous 30 days prior to the start date of this trial (or currently participating).

The principal investigator reserves the right to declare a patient ineligible or non-evaluable based on medical evidence that indicates they are unsuitable for the trial.

Pregnancy has a known effect on the stability of refractions and visual acuity. As such, subjects who become pregnant during the study will not be discontinued but their data may be excluded from analyses of effectiveness.

## 8. STUDY DESIGN

### 8.1. Study Design

This study is a single-arm, evaluator masked clinical evaluation study of refractive stability, after successful bilateral cataract surgery. Subjects will be assessed pre-operatively, operatively and at 1 month and 3 months post-operatively. Clinical evaluations will include measurement of bilateral visual acuity, manifest refraction, and defocus curve.

The primary outcome measure will be the refractive stability (spherical equivalent change  $\leq 0.50D$ ) from 1-month to 3-months.

Secondary outcome measures are as follows:

- Binocular visual acuity outcomes (uncorrected and best-distance-corrected) at distance (4-6 m) and intermediate (80 cm) at 1 month and 3 months
- Percentage of patients cumulative distribution achieving 20/20 or better, 20/25 or better, 20/30 or better and 20/40 or better intermediate vision at 80 cm

- Binocular defocus curve at 3 months

Exploratory outcome measures are as follows:

- Binocular intermediate VA (66 cm) at 3 months

### ***8.2. Methods Used to Minimize Bias***

As a single-arm study there is no expected bias. Patient selection will be based on the patient's interest and the surgeon's opinion as to whether they are a suitable candidate for IOL implantation.

Evaluators (person conducting refraction) will not have access to the 1 month data when conducting and evaluating refractive outcomes at the 3 month visit.

The measurement of visual acuity will be conducted in a systematic fashion to minimize bias. Individuals conducting visual acuity measures will be instructed to perform the same testing in the same fashion for all subjects, with the same level of encouragement to subjects.

All data collection will be completed through provided Case Report Forms (CRFs) or computer files generated by automated test equipment. All site personnel involved in the study will be trained in regard to conducting study-specific procedures.

## **9. STUDY PROCEDURE**

### ***9.1. Informed Consent / Subject enrollment***

No subject will be enrolled into the study who does not meet the inclusion/exclusion criteria and does not sign the current approved informed consent document. Informed consent will be obtained prior to collecting any data for the study. The original signed documents will be maintained by the investigator as a permanent part of the subject's medical records. A signed copy will be provided to the subject.

Subjects who complete the study will be reimbursed for the cost of their Clareon lenses.

### ***9.2. Visits and Examinations***

Subjects will participate in 7 study visits, one eye per visit for bilateral surgery. Visits will include an uptake visit, two operative visits, and 4 total postoperative visits (Visit numbers 1-5 below). The visit schedule, complete with window and associated CRF forms, are displayed in Table 9.2-1. Details of each study visit, including testing to be conducted, are provided below.

#### **Table 9.2-1. Visit Schedule**

Visit Number	Visit Name	Visit Window	CRF Number
1	Preoperative	-60 to 0 days from surgery	1
2,2a	Operative	0 from surgery	2,2a
3,3a	1 Day Postoperative	2-36 hours postoperative*	3,3a
4	1 Month Postoperative	30 ( $\pm$ 10) days postoperative**	4
5	3 Months Postoperative	90 ( $\pm$ 20) days postoperative**	5

\* relative to the operative eye

\*\* relative to the date the last eye is operated on

### 9.2.1. Preoperative

At the preoperative exam, subjects will be consented, qualified for the study (compared with inclusion/exclusion criteria), and assigned a study ID/subject number. Subject numbers will be assigned sequentially at each site in the order of enrollment. Pre-operative qualification should take place no more than 30 days prior to surgery.

A medical history will be taken and exams will include the tests described below:

- manifest refraction,
- visual acuity

In addition, all site-specific, routine, usual standard of care preoperative measures should be undertaken.

Measurements should be made as described in section 9.3 below.

### 9.2.2. Operative (Surgery)

All subjects will undergo cataract surgery with implantation of the Clareon IOL. The surgeon's usual standard of care with regard to treatment and medication will be used for all study subjects. Surgery planning and IOL power calculation will be performed using the surgeon's preferred method, with an initial a-constant provided by Alcon. The Barrett toric calculator will be used to estimate residual astigmatism.

Surgical findings will be recorded and any adverse events/serious adverse events (AEs/ SAEs) occurring during surgery will be noted at this visit. Any other problems during surgery and comments regarding surgery will be documented.

Any subject whose surgery is not completed successfully will be documented in the appropriate case report form. These subjects will be monitored for safety but clinical performance data may be excluded from the analysis.

### 9.2.3. Postoperative 1 Day

All routine, usual standard of care postoperative measures should be undertaken. In addition, the subject will undergo VA testing in accordance with the specifications below (Section 9.3). Adverse events will be monitored.

### 9.2.4. Postoperative 1 Month

All routine, usual standard of care postoperative measures should be undertaken. In addition, the subject will undergo a manifest refraction and VA testing in accordance with the specifications below (Section 9.3). Any device deficiencies or adverse events will be monitored.

### 9.2.5. Postoperative 3 Months

All routine, usual standard of care postoperative measures should be undertaken. In addition, the subject will undergo a manifest refraction, VA, and defocus curve testing in accordance with the specifications below (Section 9.3). Any device deficiencies or adverse events will be monitored.

### 9.2.6. Exit Procedures

In the event of premature exit from the study, all study related examinations should be completed where possible. The Exit CRF should be completed, noting that the subject did not complete the study and the reason for premature study exit. If no premature exit from the study occurs, the Exit CRF should be completed at the end of Visit 5 (Postoperative 3 Months).

## ***9.3. Study Methods and Measurements***

All routine testing and basic eye examinations should be carried out at each study visit. Abnormalities should be recorded in the CRF “Comment” section. Specific study examination procedures are outlined below.

### 9.3.1. Manifest Refraction

Perform a manifest refraction with a high contrast logMAR chart under photopic lighting conditions ( $>85$  cd/m^2). Document refraction results with sphere, cylinder and axis readings. If uncorrected visual acuity is not improved by manifest refraction, use zero for sphere and cylinder and draw a line through the blank for the axis.

**Note:** Each subject should be manually refracted to his/her best correction by an ophthalmologist, optometrist, or a skilled technician using a phoropter or trial lenses.

### 9.3.2. Visual Acuity (VA)

To obtain logMAR VA, ask subjects to begin reading the chart at the smallest row where all letters are easily distinguishable. Have subjects continue to read rows with smaller letters and encourage subjects to guess at all letters in a line if at least one correct response was given on the previous row. Request subjects read rows until no letters on a row are read correctly or until all letters on a row are too indistinguishable to even be guessed.

While the subject is reading the chart, record the number of letters on each line read incorrectly by the subject. The last line from which the subject read at least one letter correctly is recorded as the baseline logMAR VA. The actual logMAR VA is calculated using the baseline logMAR VA line and the number of letters read incorrectly. This VA should be recorded as the best-corrected monocular visual acuity at distance.

It is sufficient to record the uncorrected VA at distance only for the 1-day visit.

All other visual acuity testing is performed binocularly. Postoperatively conduct testing uncorrected at all visits. In addition, conduct testing with the manifest distance refraction in place at 1 month and 3 months post-operatively.

#### *Distance VA*

Measure distance visual acuity using a high contrast logMAR ETDRS chart under photopic lighting ( $>85$  cd/m^2) at a distance of 4 m.

#### *Intermediate VA*

Have the subject view an appropriately-scaled high-contrast logMAR ETDRS Visual Acuity Chart at 80 cm. Visual acuity determined with the chart will be recorded and scored.

#### *Intermediate VA*

Have the subject view an appropriately-scaled high-contrast logMAR ETDRS Visual Acuity Chart at 66 cm. Visual acuity determined with the chart will be recorded and scored. This test is only done at the 3-month visit.

### 9.3.3 Defocus Curve

Perform binocular defocus curve with a high contrast logMAR chart under photopic lighting conditions ( $>85$  cd/m^2). Conduct testing with the manifest distance refraction in place in a phoropter. Add an over-correction of +1.0 D and record binocular VA. Reduce the correction by +0.5 D and retest and record VA. Add an over-correction of -4.0 D and record VA. Remove over-correction in 0.5 D increments while testing VA at each step. The procedure ends with VA testing at a 0.0 D over-correction (best-corrected distance refraction).

#### ***9.4. Unscheduled Visits***

Unscheduled exams may be conducted at the discretion of the Investigator with all relevant information from the exam recorded in the source documents and on the Unscheduled Visit pages within the CRF booklet.

#### ***9.5. Discontinued Subjects***

Discontinued subjects are those who do not have an exit visit or who come into the office to be exited prior to the scheduled final study visit. Subjects may be discontinued from the study at any time if, in the opinion of the investigator, their continued participation in the study poses a risk to their health. The reasons for discontinuation include:

- a. Adverse event;
- b. Lost to follow-up;
- c. Subject decision unrelated to an adverse event;
- d. Protocol violation;
- e. Treatment failure;
- f. Other.

To ensure the safety of all subjects who discontinue prior to Visit 5, investigators should assess each subject and, if necessary, advise them of any therapies and/or medical procedures that might be needed to maintain their health. Any changes in medical health and/or use of concomitant medications should also be captured.

### **10. ANALYSIS PLAN**

#### ***10.1. Analysis Data Sets***

All subjects who are enrolled in the study will be evaluated for safety. Efficacy analyses will be performed based on data from those eyes where uncomplicated cataract surgery with Clareon IOL implantation was completed.

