#### ***10.2. Statistical Methodology***

A summary of the data will be prepared for all measurement time points. Summaries of the changes observed between the 1 month and 3 month post-operative visits will also be summarized.

For variables measured on a continuous scale, these summaries will include the sample size, as well as the mean, standard deviation, median, minimum, and maximum. For variables measured on a categorical scale, summaries will provide the number and percentage of subjects who provided each score (or change in scores). These summaries will be provided for all eyes completing the study.

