##### **10.2.1. Within-treatment Changes**

For variables measured on a continuous scale, the statistical significance of within-treatment changes between time points will be investigated using the TOST equivalence test.

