### ***10.3. General Statistical Considerations***

The statistical analyses will be performed using R, version 4.0.3 or higher. Any statistical tests of hypotheses will employ a level of significance of  $\alpha=0.05$ .

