## **11. SAMPLE SIZE JUSTIFICATION**

We estimate that the study would require a sample size of at least 23 patients (46 eyes) to achieve a power of 90% and a level of significance of 5% (two sided), for detecting a mean of the differences of 0.50D between pairs, and assuming the standard deviation of the differences to be 0.5. For additional power of the study and for any possible patients that leave the study prematurely, we are recommending a total of 30 patients (60 eyes)

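### The plan defines efficacy data by eye, two per subject, and gives its only test (TOST) no provision for fellow-eye correlation; run on eyes as independent, it would understate the standard error

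*Combined protocol and SAP*

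**What the plan says.** Section 7.1 sets the structure: "A total of 60 eyes of 30 subjects at one site will be enrolled. Both eyes of a subject must be enrolled".

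Section 10.1 defines the efficacy data by eye: "Efficacy analyses will be performed based on data from those eyes where uncomplicated cataract surgery with Clareon IOL implantation was completed". Section 10.2 covers the descriptive summaries, including those of the change from 1 to 3 months, and closes with "These summaries will be provided for all eyes completing the study". The same paragraph counts subjects when it describes categorical variables.

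Section 10.2.1 names the only inferential method. For continuous variables, "the statistical significance of within-treatment changes between time points will be investigated using the TOST equivalence test". It states neither the unit of the test nor an equivalence margin. Section 10.3 sets alpha at 0.05 for any hypothesis test and does not say whether this applies to each one-sided test or is split between the two.

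Sections 10 and 11 mention no averaging within subject, random subject effect, GEE, clustered variance, inter-eye correlation or design effect.

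**The concern.** Spherical equivalent change is measured in each eye, so each subject supplies two values. Table 9.2-1 times the 1-month and 3-month visits from surgery on the last eye, and Table 15.1 states that visits are by patient with both eyes tested. Both changes therefore come from the same two visits by the same person. Whatever the patient, session or examiner contributes to one eye's change can also enter the other's, so a positive correlation is plausible.

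A standard TOST on eye-level changes assumes independent observations. With positively correlated pairs, its standard error is too small and the interval behind it too narrow. Mean refraction could then be declared stable more often than the nominal level allows when the true mean change is at the margin. This matters because it is the plan's only named test and it would be applied to the variable underlying the primary outcome. Leaving the unit open also leaves an analytic choice to be made after the data are seen.

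**Working it through.** **Inputs from the documents.** 30 subjects, 60 eyes (Section 7.1); alpha 0.05 (10.3); SD of the differences 0.5 D (11).

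**Assumed, because not given.** Correlation rho between fellow-eye changes: 0.3, 0.5 and 0.7 as a range. TOST margin: 0.50 D, borrowed from the primary outcome threshold. Alpha per side: 0.05, with 0.025 as the alternative.

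**1. The plan's own figure.** Section 11 asks for "at least 23 patients (46 eyes) to achieve a power of 90% and a level of significance of 5% (two sided"). Its inputs are a mean paired difference of 0.50 D and an SD of 0.5 D. The paired formula gives (1.960 + 1.282)² × (0.5/0.5)² = 10.5, so 11 pairs; the exact paired t-test needs 13 (power 91.1%). A TOST with margin 0.50 D and true change 0 needs 13 units at 0.05 per side, or 16 at 0.025. None of these gives 23. A two-independent-group t-test gives 23 per group, 46 in total (power 91.2%), but that is not the paired design described. The mismatch is a separate matter. What counts here is that no inter-eye correlation enters the calculation.

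**2. Standard error.** For n subjects with two eyes each, Var(mean) = (SD²/2n)(1 + rho). The correct standard error is therefore sqrt(1 + rho) times the naive one, and the effective number of eyes is 60/(1 + rho).

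**3. False-equivalence rate at the margin.** With 0.05 per side the rate is 1 − Phi(1.645/sqrt(1 + rho)). With 0.025 per side, 1.960 replaces 1.645.

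| rho | SE ratio | Effective eyes | Rate, 0.05 per side | Rate, 0.025 per side |
|---|---|---|---|---|
| 0 | 1.00 | 60 | 5.0% | 2.5% |
| 0.3 | 1.14 | 46 | 7.5% | 4.3% |
| 0.5 | 1.22 | 40 | 9.0% | 5.5% |
| 0.7 | 1.30 | 35 | 10.4% | 6.6% |
| 1.0 | 1.41 | 30 | 12.2% | 8.3% |

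With 0.025 per side, the rate passes 5% when (1.960/1.645)² − 1 < rho, that is, above about 0.42. Simulation of the t-based TOST with 30 subjects (50,000 runs per setting, 0.05 per side) gives 7.4%, 9.2% and 10.5% at rho 0.3, 0.5 and 0.7. A TOST on subject means gives 4.8% to 5.2% across rho from 0 to 1.

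**4. How often the verdict would differ.** Take SD 0.5 D, margin 0.50 D and 0.05 per side. The eye-level TOST passes if the absolute observed mean change is below 0.50 − 1.671 × 0.5/sqrt(60) = 0.392 D. The subject-mean TOST passes below 0.50 − 1.699 × 0.5 × sqrt((1 + rho)/60) = 0.375, 0.366 and 0.357 D at rho 0.3, 0.5 and 0.7. The two disagree only in a band 0.017 to 0.035 D wide.

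**5. Power after correction.** With a true change of 0 and fully correlated eyes, the subject-level TOST has power of about 99.7% with 23 subjects and over 99.9% with 30 (0.05 per side). At 0.025 per side the figures are 99.1% and 99.9%.

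**The case against.** The strongest objection is that the unit of the TOST is inferred. Section 10.1 says which eyes supply data, and a subject-mean or mixed-model analysis would also draw on those eyes. The all-eyes sentence in 10.2 governs descriptive summaries. This stands in part. A reader might infer that the plan commits to an eye-level TOST with an understated standard error, but 10.2.1 does not say so. What the documents support is that the text points to eyes and contains nothing that would stop such an analysis.

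A reader might also infer that the false-equivalence rate exceeds 5% whatever else holds. The documents do not support this. Rho, the margin and the alpha per side are all unstated. Rho concerns change scores, and differencing removes stable subject effects, so the larger assumed values have no direct backing. With 0.05 per side any positive rho takes the rate above 5%; with 0.025 per side only rho above about 0.42 does.

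The practical effect is limited, and this stands. The inflated rates apply when the true mean change is at the margin. With a true mean of 0 to 0.1 D, both versions pass more than 99.8% of the time at rho 0.5 to 0.7. With a true mean of 0.50 D, SD 0.5 D and normal changes, only about 48% of eyes would change by 0.50 D or less (Phi(0) − Phi(−2) = 0.477). A false TOST pass would then sit beside a responder result far from the 80% of subjects in the hypothesis.

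Finally, a reader might extend the point to the responder outcome, the secondary outcomes or 95% intervals. The TOST is limited to continuous variables and does not test the 80% hypothesis. All the secondary outcomes are binocular, with one value per subject. Section 10.2 lists no confidence intervals.

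**Conclusion.** The concern holds as a gap in specification with a definite direction: the plan points to eyes as the unit and does not provide for fellow-eye correlation. An eye-level TOST that assumes independence understates the standard error by a factor sqrt(1 + rho) for any positive rho, or 1.14 to 1.30 for rho from 0.3 to 0.7. The false-equivalence rates tabulated above are conditional on an assumed rho and on the alpha per side; they hardly depend on the margin. The narrow band of disagreement, by contrast, rests on the assumed 0.50 D margin and the plan's SD of 0.5 D.

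Severity is should-fix. The nominal level is not assured for the plan's only named test, but the conclusion is unlikely to change if the true mean change is well inside the margin.

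**What to change.** In Section 10.2.1, state that the TOST on spherical equivalent change is computed in one of two ways:

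- on one value per subject, the mean 1-to-3-month change of that subject's evaluable eyes (n up to 30); or
- from a linear mixed model on eye-level changes with a random subject intercept.

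Name one as primary. They differ when some subjects contribute a single eye, which Section 10.1 allows because it admits eyes individually. In the same place, state the equivalence margin and the alpha for each one-sided test (equivalently, the confidence level of the interval), and say that binocular measures have n equal to the number of subjects.

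The cost is a few sentences and no new data. The interval becomes somewhat wider, with negligible loss of power under the plan's SD of 0.5 D and a 0.50 D margin.
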